5.2 Requirements Prior to Administration of the Second and Third Vaccinations

The following assessments should be performed prior to the administration of the second and third vaccinations to determine if the subject remains eligible:

Subjects will not receive the subsequent vaccine doses (first or second boost) if any of the prespecified individual halting criteria are met (see below and Section 8.6.2).

- For a woman of childbearing potential, an acceptable form of birth control must be verified. A urine pregnancy test must be performed and the subject must not be pregnant before administering the vaccine.
- Subjects who do not meet inclusion criteria 2 4 and 7 11, and exclusion criteria 7 21 will not be given the second or third vaccination.
- Subjects who have a fever (defined as an oral temperature ≥38.0°C) or a moderate or severe acute illness at the time of or in the three days prior to boost vaccination administration may have the boost vaccination deferred until they recover as long as this remains within the study window (see Section 6.3).
- Subjects who do not receive the second dose of vaccine for any reason will not receive the third dose of vaccine.

5.3 Withdrawal from the Study, Discontinuation of Study Product, or Study Termination

5.3.1 Withdrawal from the Study or Discontinuation of the Study Product

Subjects may voluntarily withdraw their consent for study participation at any time without penalty or loss of benefits to which they are otherwise entitled.

DMID/NIAID/NIH

An investigator may also withdraw a subject from receiving the study product for any reason. Follow-up safety evaluations and blood draws will be conducted, if the subject agrees. If a subject withdraws or is withdrawn prior to completion of the study, the reason for this decision must be recorded in the electronic case report forms (eCRFs).

The reasons, might include, but are not limited to the following:

- Subject no longer meets eligibility criteria
- Subject meets individual halting criteria (reference to Section 8.6.2)
- Subject becomes noncompliant
- Medical disease or condition, or new clinical finding(s) for which continued participation, in the opinion of the investigator might compromise the safety of the subject, interfere with the subject's successful completion of this study, or interfere with the evaluation of responses
- Subject lost to follow-up
- Subject becomes pregnant, if applicable
- Determined by a physician's discretion to require additional therapy not indicated in the protocol to ensure subject's health and well-being (or treatment failure, if applicable)

The investigator should be explicit regarding study follow-up (e.g. safety follow-up) that might be carried out despite the fact the subject will not receive further study product. If the subject consents, every attempt will be made to follow all AEs through resolution. The procedures that collect safety data for the purposes of research must be inclusive in the original informed consent or the investigator may seek subsequent informed consent using an IRB/IEC-approved consent form with the revised procedures.

The investigator will inform the subject that already collected data will be retained and analyzed even if the subject withdraws from this study.

5.3.2 Subject Replacement

Subjects who withdraw, or are withdrawn or terminated from this trial, or are lost to follow-up after signing the informed consent form (ICF), randomization and receipt of study vaccine will not be replaced. However, if a subject withdraws after signing the ICF, but before randomization and/or receipt of study vaccine, they may be replaced.

DMID/NIAID/NIH

5.3.3 Study Termination

If the study is prematurely terminated by the sponsor, any regulatory authority, the IRB, or the investigator for any reason, the investigator will promptly inform the study subjects and assure appropriate therapy or follow-up for the subjects, as necessary. If the DMID agrees, then other study procedures (e.g., safety follow-up, blood sampling for safety and immunogenicity) may be continued through the remaining study visits but no further vaccinations will occur. The investigator will provide a detailed written explanation of the termination to the IRB/IEC.

DMID/NIAID/NIH

6 STUDY PROCEDURES

6.1 Screening Visit: Visit 00 (Day -28 to -1, All Groups)

Up through 28 days before baseline (the day of the subject's prime vaccination, Day 1), screening assessments as indicated in Sections 5.1.1 and 5.1.2 will occur. Screening may be split into multiple days or visits.

The ICF will be signed before any study-specific procedures at the start of the screening period (see Section 9.2). For women of childbearing potential, it should be confirmed that adequate birth control measures were used from at least 28 days before the prime vaccination with a negative serum β -human chorionic gonadotropin (β -hCG) pregnancy test available before Day 1 and a negative urine β -hCG pregnancy test immediately (within 24 hours) prior to each study vaccination. All women, except for those of non-childbearing potential, will be asked to use adequate birth control from signing of the ICF onwards until at least 3 months after the last boost vaccination.

The investigator will provide detailed information on the study to the subject and will obtain written informed consent prior to each subject's study participation. The procedures indicated in **Section 7** will only be performed after the subject's written informed consent has been obtained.

The following assessments are performed during the Screening Visit to determine eligibility requirements as specified in the inclusion and exclusion criteria (Section 5.1.1 and 5.1.2). The written informed consent must be signed prior to conducting any of the assessments listed below:

- Obtain medical history (see Section 7.1.1)
- Review prestudy medications and therapies up to 30 days prior to start of screening and record on the eCRF.
- Measure vital signs (HR, BP, and oral body temperature). This will also include height and weight for determination of BMI.
- Perform abbreviated physical examination. This will be done by a licensed clinician listed on FDA Form 1572.
- Review of birth control history with female subjects.
- Counsel subjects to use adequate birth control methods to avoid pregnancy

DMID/NIAID/NIH

- Obtain blood and urine for baseline screening laboratories (see Section 2.3.1 for additional details).
- Review inclusion and exclusion criteria

Laboratory values will be determined according to the Appendix B Toxicity Table.

The overall eligibility of the subject to participate in the study will be assessed once all screening values and results of any other required evaluations are available. Retesting of values (e.g., baseline screening laboratories) that lead to exclusion is allowed **once** using an unscheduled visit during screening to assess eligibility, provided there is an alternative explanation for the out of range value. Study subjects who qualify for inclusion will be contacted and scheduled for enrollment and prime vaccination within the window for enrollment.

6.2 Enrollment/Baseline: Visit 01, Day 1, Vaccination Clinic Visit (All Groups)

The investigator should ensure that all enrollment criteria have been met during screening. If a subject's status (including any unscheduled laboratory results or the receipt of additional medical records) after screening but before the prime vaccination changes such that the subject no longer meets all enrollment criteria, then the subject should be excluded from participation in the study.

If the initial laboratory screening occurred more than 28 days before baseline (Day 1) but the subject was unable to be vaccinated within the 28-day window (e.g., due to meeting **Exclusion Criteria** in **Section 5.1.2** or for other reasons), the subject must have safety laboratories repeated (see protocol-specific MOP for details about laboratories).

Prior to Vaccination

- Review inclusion and exclusion criteria to ensure the subject remains eligible for enrollment
- Review medical history for any interval changes
- Review prestudy and concomitant medications
- Obtain vital signs (HR, BP, and oral temperature)
- Subjects who have a diastolic blood pressure value >90 mmHg or a systolic blood pressure value >140 mmHg prior to the prime vaccination can receive the vaccination if the elevated blood pressure is considered to be not clinically significant and the subject had acceptable blood pressure at screening.

- Perform symptom-directed PE (if needed).
- Perform urine pregnancy test for women of childbearing potential within 24 hours prior to immunization. Test result must be known and negative prior to vaccination.
- Review of birth control history with female subjects
- Counsel subjects to use adequate birth control methods to avoid pregnancy
- Subjects will be enrolled in Advantage eClinical[®] and randomly assigned to a Study Group (see Section 10.3.1 Randomization Procedures for details).
- Obtain serum for immunogenicity assays.
- Collect PBMCs and plasma for future assays.
- Study vaccine will be prepared on-site by an unblinded site research pharmacist (see Section 4.3).
- Pre-administration reactogenicity assessments will be performed prior to the first study vaccination to establish baseline. A subject with mild pre-administration reactogenicity which is transient, resolving, or clinically insignificant may receive vaccination at the investigator's discretion.

Vaccination

- The unblinded study vaccine administrator will vaccinate the subject according to vaccination assignment in the subject's preferred arm.
- Following receipt of study product, subjects may have the injection site covered with an adhesive bandage (e.g. BAND-AID®) as needed.

Following Vaccination

- Observe subjects for a minimum of 30 minutes following immunization.
- Provide subjects with the e-Memory aid instructions, ruler and thermometer and instruct the subject on the observance, grading and recording of unsolicited reactions and solicited injection site reactions, systemic reactions and daily maximum temperatures through Day 8, beginning with the day of vaccination (Day 1). Subjects will be instructed on how to complete the e-Memory aid. Reactions that persist beyond Day 8 will continue to be recorded

DMID/NIAID/NIH

until the subject is symptom-free. As a back-up method in the event of internet connectivity issues, subjects will also be provided a paper memory aid.

- Instruct subjects as to when to contact the investigator about unsolicited AEs.
- Review hypersensitivity symptoms with the subject and counsel to contact study personnel or seek medical attention immediately.
- Post-administration reactogenicity assessments will be performed, vital signs will be obtained, and the vaccination site assessed at a minimum of 30 minutes following immunization.
- Evaluate vaccination site.
- Solicited and Unsolicited AEs, and SAEs will be collected and documented on the eCRFs, together with the information on any concomitant medications.

6.3 Planned Study Visits

6.3.1 Follow-up

6.3.1.1 Visit 02, Day 4 +/- 1 Day; Telephone Call

- Interview the subject and review the e-Memory aid data. Address any incomplete, missing, or inconsistent data.
- Review of Unsolicited AEs and SAEs.
- Review concomitant medications

6.3.1.2 Visit 03, Day 8 +/- 1 Day; Clinic Visit

- Obtain vital signs (HR, BP, and oral temperature)
- Perform symptom-directed PE (if needed)
- Evaluate vaccination site
- Interview the subject and review the e-Memory aid data. Address any incomplete, missing, or inconsistent data.
- Review of Unsolicited AEs and SAEs.

DMID/NIAID/NIH

- If symptoms persist, clinic staff will attempt to follow up with the subject until the symptoms resolve. Maximum severity post Day 8 and stop date of the symptoms will be recorded by clinic staff on the Solicited Events eCRF.
- Counsel subjects to use adequate birth control methods to avoid pregnancy
- Review concomitant medications.
- Obtain blood for safety laboratories (Section 2.3.1).
- Obtain serum for immunogenicity assays
- Collect PBMCs and plasma for future assays.

6.3.1.3 Visit 04, Day 15 +/- 2 Days; Clinic Visit

- Obtain vital signs (HR, BP, and oral temperature)
- Perform symptom-directed PE (if needed)
- Evaluate vaccination site (if needed)
- Interview the subject and review the e-Memory aid data. Address any incomplete, missing, or inconsistent data.
- Review of Unsolicited AEs and SAEs.
- Counsel subjects to use adequate birth control methods to avoid pregnancy
- Review concomitant medications.
- Obtain blood for safety laboratories (if needed due to abnormalities at prior visit, Section 2.3.1)
- Obtain serum for immunogenicity assays
- Collect PBMCs and plasma for future assays.

6.3.1.4 Visit 05, Day 29 +/- 2 Days; Clinic Visit

Prior to Vaccination

• Review medical history for any interval changes

DMID/NIAID/NIH

CONFIDENTIAL

DMID eCTD Compliant Interventional Protocol Template and Instructions, Version 4.0, Dated May 15, 2018

- Review concomitant medications
- Obtain vital signs (HR, BP, and oral temperature)
- Subjects who have a diastolic blood pressure value >90 mmHg or a systolic blood pressure value >140 mmHg prior to the prime vaccination can receive the vaccination if the elevated blood pressure is considered to be not clinically significant and the subject had acceptable blood pressure at screening.
- Perform symptom-directed PE (if needed)
- Perform urine pregnancy test for women of childbearing potential within 24 hours prior to immunization. Test result must be known and negative prior to vaccination.
- Review of birth control history with female subjects.
- Counsel subjects to use adequate birth control methods to avoid pregnancy.
- Obtain serum for immunogenicity assays.
- Collect PBMCs and plasma for future assays.
- Review inclusion and exclusion criteria to ensure the subject remains eligible for boost vaccination.
- Study vaccine will be prepared on-site by an unblinded site research pharmacist (see Section 4.3).
- Pre-administration reactogenicity assessments will be performed prior to vaccination to establish baseline. A subject with mild pre-administration reactogenicity which is transient, resolving, or clinically insignificant may receive vaccination at the investigator's discretion.

Vaccination

- The unblinded study vaccine administrator will vaccinate the subject according to vaccination assignment in the subject's preferred arm.
- Following receipt of study product, subjects may have the injection site covered with an adhesive bandage (e.g. BAND-AID®) as needed.

Following Vaccination

DMID/NIAID/NIH

- Observe subjects for a minimum of 30 minutes following immunization.
- Provide subjects with the e-Memory aid instructions, ruler and thermometer and instruct the subject on the observance, grading and recording of unsolicited reactions and solicited injection site reactions, systemic reactions and daily maximum temperatures through Day 8, beginning with the day of vaccination (Day 1). Subjects will be instructed on how to complete the e-Memory aid. Reactions that persist beyond Day 8 will continue to be recorded until the subject is symptom-free. As a back-up method in the event of internet connectivity issues, subjects will also be provided a paper memory aid.
- Instruct subjects as to when to contact the investigator about unsolicited AEs.
- Review hypersensitivity symptoms with the subject and counsel to contact study personnel or seek medical attention immediately.
- Post-administration reactogenicity assessments will be performed, vital signs will be obtained, and the vaccination site assessed at a minimum of 30 minutes following immunization.
- Evaluate vaccination site.
- Solicited and Unsolicited AEs and SAEs will be collected and documented on the eCRFs, together with the information on any concomitant medications.

6.3.1.5 Visit 06, Day 32 (Day 4 after First Boost; +/- 1 Day); Telephone Call

- Interview the subject and review the e-Memory aid data. Address any incomplete, missing, or inconsistent data.
- Review of Unsolicited AEs and SAEs.
- Review concomitant medications

6.3.1.6 Visit 07, Day 36 (Day 8 after First Boost; +/- 1 Day); Clinic Visit

- Obtain vital signs (HR, BP, and oral temperature)
- Perform symptom-directed PE (if needed)
- Evaluate vaccination site

DMID/NIAID/NIH

CONFIDENTIAL

DMID eCTD Compliant Interventional Protocol Template and Instructions, Version 4.0, Dated May 15, 2018

- Interview the subject and review the e-Memory aid data. Address any incomplete, missing, or inconsistent data.
- Review of Unsolicited AEs and SAEs.
- If symptoms persist, clinic staff will attempt to follow up with the subject until the symptoms resolve. Maximum severity post boost Day 8 and stop date of the symptoms will be recorded by clinic staff on the Solicited Events eCRF.
- Counsel subjects to use adequate birth control methods to avoid pregnancy
- Review concomitant medications.
- Obtain blood for safety laboratories (Section 2.3.1).
- Obtain serum for immunogenicity assays
- Collect PBMCs and plasma for future assays.

6.3.1.7 Visit 08, Day 43 (Day 15 after First Boost; +/- 2 Days); Clinic Visit

- Obtain vital signs (HR, BP, and oral temperature)
- Perform symptom-directed PE (if needed)
- Evaluate vaccination site (if needed)
- Interview the subject and review the e-Memory aid data. Address any incomplete, missing, or inconsistent data.
- Review of Unsolicited AEs and SAEs.
- Counsel subjects to use adequate birth control methods to avoid pregnancy
- Review concomitant medications.
- Obtain blood for safety laboratories (if needed due to abnormalities at prior visit, Section 2.3.1)
- Obtain serum for immunogenicity assays
- Collect PBMCs and plasma for future assays.

6.3.1.8 Visit 09, Day 57 (Day 29 after First Boost; +/- 2 Days); Clinic Visit

- Perform symptom-directed PE (if needed)
- Review of Unsolicited AEs and SAEs.
- Counsel subjects to use adequate birth control methods to avoid pregnancy
- Review concomitant medications.
- Obtain serum for immunogenicity assays
- Collect PBMCs and plasma for future assays.

6.3.1.9 Visit 10, Day 120 (Day 92 after First Boost; +/- 14 Days); Telephone Call

- Review of SAEs.
- Review concomitant medications if associated with an SAE.
- Counsel subjects to use adequate birth control methods to avoid pregnancy

6.3.1.10 Visit 11, Day 180 +/- 14 Days from Prime Vaccination; Clinic Visit

Prior to Vaccination

- Review medical history for any interval changes
- Review concomitant medications
- Obtain vital signs (HR, BP, and oral temperature)
- Subjects who have a diastolic blood pressure value >90 mmHg or a systolic blood pressure value >140 mmHg prior to the prime vaccination can receive the vaccination if the elevated blood pressure is considered to be not clinically significant and the subject had acceptable blood pressure at screening.
- Perform symptom-directed PE (if needed).
- Perform urine pregnancy test for women of childbearing potential within 24 hours prior to immunization. Test result must be known and negative prior to vaccination.
- Review of birth control history with female subjects.

DMID/NIAID/NIH

- Counsel subjects to use adequate birth control methods to avoid pregnancy.
- Obtain blood for safety laboratories (Section 2.3.1).
- Obtain serum for immunogenicity assays.
- Collect PBMCs and plasma for future assays
- Review inclusion and exclusion criteria to ensure the subject remains eligible for boost vaccination
- Study vaccine will be prepared on-site by an unblinded site research pharmacist (see Section 4.3).
- Pre-administration reactogenicity assessments will be performed prior to vaccination to establish baseline. A subject with mild pre-administration reactogenicity which is transient, resolving, or clinically insignificant may receive vaccination at the investigator's discretion.

Vaccination

- The unblinded study vaccine administrator will vaccinate the subject according to vaccination assignment in the subject's preferred arm.
- Following receipt of study product, subjects may have the injection site covered with an adhesive bandage (e.g. BAND-AID®) as needed.

Following Vaccination

- Observe subjects for a minimum of 30 minutes following immunization.
- Provide subjects with the e-Memory aid instructions, ruler and thermometer and instruct the subject on the observance, grading and recording of unsolicited reactions and solicited injection site reactions, systemic reactions and daily maximum temperatures through Day 8, beginning with the day of vaccination (Day 1). Subjects will be instructed on how to complete the e-Memory aid. Reactions that persist beyond Day 8 will continue to be recorded until the subject is symptom-free. As a back-up method in the event of internet connectivity issues, subjects will also be provided a paper memory aid.
- Instruct subjects as to when to contact the investigator about unsolicited AEs.

- Review hypersensitivity symptoms with the subject and counsel to contact study personnel or seek medical attention immediately.
- Post-administration reactogenicity assessments will be performed, vital signs will be obtained, and the vaccination site assessed at a minimum of 30 minutes following immunization.
- Evaluate vaccination site.
- Solicited and Unsolicited AEs and SAEs will be collected and documented on the eCRFs, together with the information on any concomitant medications.

6.3.1.11 Visit 12, Day 184 (Day 4 after Second Boost; +/- 1 Day); Telephone Call

- Interview the subject and review the e-Memory aid data. Address any incomplete, missing, or inconsistent data.
- Review of Unsolicited AEs and SAEs.
- Review concomitant medications

6.3.1.12 Visit 13, Day 187 (Day 8 after Second Boost; +/- 1 Day); Clinic Visit

- Obtain vital signs (HR, BP, and oral temperature)
- Perform symptom-directed PE (if needed)
- Evaluate vaccination site
- Interview the subject and review the e-Memory aid data. Address any incomplete, missing, or inconsistent data.
- Review of Unsolicited AEs and SAEs.
- If symptoms persist, clinic staff will attempt to follow up with the subject until the symptoms resolve. Maximum severity post boost Day 8 and stop date of the symptoms will be recorded by clinic staff on the Solicited Events eCRF.
- Counsel subjects to use adequate birth control methods to avoid pregnancy
- Review concomitant medications.

DMID/NIAID/NIH

CONFIDENTIAL

DMID eCTD Compliant Interventional Protocol Template and Instructions, Version 4.0, Dated May 15, 2018

- Obtain blood for safety laboratories (Section 2.3.1).
- Obtain serum for immunogenicity assays
- Collect PBMCs and plasma for future assays.

6.3.1.13 Visit 14, Day 194 (Day 15 after Second Boost; +/- 2 Days); Clinic Visit

- Obtain vital signs (HR, BP, and oral temperature)
- Perform symptom-directed PE (if needed)
- Evaluate vaccination site (if needed)
- Interview the subject and review the e-Memory aid data. Address any incomplete, missing, or inconsistent data.
- Review of Unsolicited AEs and SAEs.
- Counsel subjects to use adequate birth control methods to avoid pregnancy
- Review concomitant medications.
- Obtain blood for safety laboratories (if needed due to abnormalities at prior visit, Section 2.3.1).
- Obtain serum for immunogenicity assays
- Collect PBMCs and plasma for future assays.

6.3.1.14 Visit 15, Day 208 (Day 29 after Second Boost; +/- 2 Days); Clinic Visit

- Perform symptom-directed PE (if needed)
- Review of Unsolicited AEs and SAEs.
- Counsel subjects to use adequate birth control methods to avoid pregnancy
- Review concomitant medications.
- Obtain serum for immunogenicity assays
- Collect PBMCs and plasma for future assays.

DMID/NIAID/NIH

CONFIDENTIAL

DMID eCTD Compliant Interventional Protocol Template and Instructions, Version 4.0, Dated May 15, 2018

6.3.1.15 Visit 16, Day 270 (Day 90 after Second Boost; +/- 14 Days); Telephone Call

- Review of SAEs.
- Review concomitant medications if associated with an SAE.

6.3.2 Final Study Visit: Visit 17, Day 360 +/- 28 days (Day 180 after Second Boost); Clinic Visit

- Perform symptom-directed PE (if needed)
- Review of SAEs.
- Review concomitant medications if associated with an SAE.
- Obtain serum for immunogenicity assays
- Collect PBMCs and plasma for future assays.

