2.3 Potential Risks and Benefits

2.3.1 Potential Risks

The potential risks of participating in this trial are those associated with having blood drawn, the IM injection and possible reactions to the HEV-239 vaccine with aluminum adjuvant, and breach of confidentiality.

Drawing blood may cause transient discomfort and fainting. Fainting is usually transient and managed by having the subject lie down and elevate his/her legs. Bruising at the blood draw site may occur but can be prevented or lessened by applying pressure to the blood draw site for a few minutes after the blood is taken. IM injection may also cause transient discomfort and fainting. Drawing blood and IM injection may cause infection. The use of aseptic (sterile) technique will make infection at the site where blood will be drawn or where the study vaccination will be given extremely unlikely.

There is a small amount of risk to subjects who report that they are in good health but who may have an unknown health problem at the time of screening. This trial will screen by physical exam, history, and vital signs. The following baseline laboratories will be obtained at screening on all subjects to determined eligibility.

Baseline Laboratories:

- Hematology
 - Complete blood count with differential (which will include white blood cells, the absolute neutrophil count (ANC), the absolute eosinophil count (AEC), hemoglobin, and platelets).
 - A WBC evaluation may include any abnormal cells, which will then be reported by the laboratory. A hematology evaluation may include abnormalities in the red blood cell (RBC) count and/or RBC parameters

DMID/NIAID/NIH

CONFIDENTIAL

and/or RBC morphology, which will then be reported by the laboratory. In addition, any other abnormal cells in a blood smear will also be reported.

- Chemistry (fasting or non-fasting)
 - o Creatinine
 - o Glucose
 - Alanine aminotransferase (ALT)
- Serology
 - Hepatitis B surface antigen
 - Hepatitis C antibody
 - HIV types 1 and 2 antigen/antibody
 - Hepatitis E virus IgM and IgG antibodies
- Serum pregnancy test (in women of childbearing potential)
- Urine
 - A urine drug screen will be obtained

Safety laboratories will be obtained on Day 8 after each vaccine dose and also before the Day 180 vaccination. To minimize risks, subjects will not receive the subsequent study vaccinations if a related Grade 3 laboratory abnormality occurs. The following safety laboratories will be obtained on all subjects to determined safety.

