7.2.2.2 Laboratory Specimen Shipping

Specimen shipment will occur at intervals during the course of this trial following all applicable International Air Transport Association (IATA) requirements and according to the specifics for storage temperature and documentation as detailed in the central (clinical) laboratory manual and protocol-specific MOP as appropriate.

Specimens for safety laboratory evaluation will be shipped from the Emory VTEU to the clinical laboratory.

Screening: Specimens for initial immunogenicity laboratory evaluations at screening will be sent to the Emory VTEU laboratory in an unblinded manner. Results will be conveyed back to the Emory VTEU clinical team.

Enrolled Subjects: Specimens for immunogenicity laboratory evaluations beginning Day 1 and continuing throughout the study will be shipped from the Emory VTEU to the central repository and then provided by the DMID CMS to Emory VTEU laboratory in a blinded manner.

Further instructions for specimen shipment are included in the central (clinical) laboratory manual and protocol-specific MOP, as appropriate.

DMID/NIAID/NIH

CONFIDENTIAL

Phase I Study of HEV-239

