8.6.2 Individual Halting Criteria

Individual subjects will not be administered boost vaccination doses (2nd or 3rd vaccination) if he or she experiences ANY of the following:

- Anaphylaxis within 1 day after administration of a study vaccine.
- Allergic reaction (e.g., generalized urticaria) within 3 days after administration of a study vaccine.
- A serious adverse event (SAE) that is considered to be study vaccine-related.
- A severe (grade 3) laboratory adverse event that is considered to be study vaccine-related and persists for 3 or more days.
- A severe (grade 3) unsolicited adverse event that is considered to be study vaccine-related and does not resolve or decrease to a lower grade.

DMID/NIAID/NIH

DMID Protocol 15-0108	Version 2.0
Phase I Study of HEV-239	08 FEB 2019

- A severe (grade 3) solicited systemic adverse event that is considered to be study vaccinerelated and persists for 3 or more days and does not resolve or decrease to a lower grade (Subjective systemic reaction corroborated by study personnel).
- A severe (grade 3) solicited injection site adverse event that persists for 3 or more days and does not resolve or decrease to a lower grade. (The size [measured in mm] of ecchymosis, erythema, and induration/swelling will not be used as a halting criterion).

Vaccinations for an individual subject may be suspended for safety concerns other than those described above, at the discretion of the investigator if he/she feels the subject's safety may be threatened. The investigator may ask for an *ad hoc* SMC meeting to be held for any single event or combination of multiple events which, in his/her professional opinion, could jeopardize the safety of the subjects or the reliability of the data.

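### Protocol 2.3.1 and 8.6.2 give different laboratory rules for withholding further doses, and no passage ensures that the Day 180 safety sample is reviewed before Dose 3.

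*Protocol*

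**What the plan says.** **The rule for withholding doses.** Protocol 2.3.1 sets the laboratory timing: "Safety laboratories will be obtained on Day 8 after each vaccine dose and also before the Day 180 vaccination". The next sentence reads: "To minimize risks, subjects will not receive the subsequent study vaccinations if a related Grade 3 laboratory abnormality occurs". Protocol 8.6.2 lists, among the reasons for withholding the second or third vaccination, "A severe (grade 3) laboratory adverse event that is considered to be study vaccine-related and persists for 3 or more days". SAP 6.6 repeats the 8.6.2 form.

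**The Day 180 sample.** Protocol 6.3.1.10 (Visit 11) includes "Obtain blood for safety laboratories (Section 2.3.1" among the tasks done before vaccination at the Dose 3 visit. Appendix A likewise marks the Day 180 hematology and chemistry draw as pre-dose. The urine pregnancy test in the same Visit 11 list carries a further sentence: "Test result must be known and negative prior to vaccination". The laboratory line carries none.

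**Other places where a result check might sit.**
- Section 5.2 (requirements before the second and third vaccinations) refers to the individual halting criteria. It re-applies inclusion criteria 2 to 4 and 7 to 11, and so leaves out criterion 5, the screening laboratory values.
- Section 7.2.1.2 requires a clinician to review laboratory reports but sets no deadline relative to dosing.
- Section 7.2.2.2 says "Specimens for safety laboratory evaluation will be shipped from the Emory VTEU to the clinical laboratory" and gives no turnaround time.

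**The concern.** A rule for withholding vaccine should give one answer for one set of facts. Here the risk section and the halting section give two, and site staff could follow either in good faith. The SAP carries only one of them.

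The second difficulty concerns the Day 180 sample. Section 2.3.1 names it together with Day 8 after each dose and then states the bar on later doses. Dose 3 is the only vaccination left for that sample to affect. If the injection may go ahead before the result is read, the sample may not do what its placement in 2.3.1 suggests.

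The interval before Dose 3 is also thinly observed. Under section 8.2, non-serious unsolicited events are not collected between Day 57 and Day 180. The Day 120 call (6.3.1.9) reviews only serious events. Day 180 is the only scheduled laboratory sample between the Day 36 sample, with its optional Day 43 repeat, and Dose 3.

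**Working it through.** The plan gives no figure on this point, so there is none to reproduce. The check compares the passages and then works out the timing.

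**1. The two rules applied to the same subject**

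| Related Grade 3 laboratory value | Protocol 2.3.1 | Protocol 8.6.2 and SAP 6.6 |
|---|---|---|
| Shown to last 3 days or more | further doses barred | further doses barred |
| Below Grade 3 again in less than 3 days | further doses barred | not barred by this criterion |
| Seen in one sample, not yet repeated | further doses barred | criterion not shown to be met |

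The rules agree only in the top row. For the middle row, take an ALT above 175 U/L on Day 8 (Grade 3 in Appendix B), judged related, that is below Grade 3 in an unscheduled repeat less than 3 days later. Section 2.3.1 bars Dose 2 for that subject; the 8.6.2 laboratory criterion does not. The bottom row is the position of a new abnormality in the Day 180 sample: one same-day draw cannot show persistence, even if the result is back.

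**2. Is the Day 180 result required before Dose 3?**

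- 6.3.1.10 and Appendix A fix the time of the draw, not of the result.
- 5.2 lists no check of current laboratory values.
- 7.2.1.2 requires review, with no deadline.
- 7.2.2.2 ships the sample, with no turnaround time.
- The pregnancy test at the same visit does carry a result-known condition, so the protocol states such a condition where it intends one.

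On purpose: the laboratory endpoint in 3.3.1 is Day 8 after each vaccination, and SAP 3.3 defines baseline as the last value before the first dose. The SAP by-visit laboratory table shells have rows for Baseline and Days 8, 36 and 187 but none for Day 180; only Figures 21 to 27 plot it by visit. The risk-minimisation text in 2.3.1 is therefore the nearest thing to a stated reason for the draw. This is an inference, because the protocol does not say so outright.

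**3. Age of the last mandatory result that can be relied on before Dose 3**

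Inputs from Protocol 6.3 and Appendix A: Dose 2 at Day 29 ± 2; Visit 07 at Day 8 after Dose 2 (Dose 2 day + 7) ± 1; Dose 3 at Day 180 ± 14.

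- Nominal: 180 − 36 = 144 days.
- Shortest: Dose 3 at 180 − 14 = Day 166; Visit 07 at 29 + 2 + 7 + 1 = Day 39; 166 − 39 = 127 days.
- Longest: Dose 3 at 180 + 14 = Day 194; Visit 07 at 29 − 2 + 7 − 1 = Day 33; 194 − 33 = 161 days.
- If the optional Day 43 repeat is taken: 180 − 43 = 137 days nominal.

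For comparison, the Day 8 sample precedes Dose 2 by 29 − 8 = 21 days nominal, so its result can reasonably be available.

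**4. Who is exposed**

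Up to 20 + 5 = 25 subjects are due Dose 3. The number is smaller if any miss Dose 2, because 5.2 then withholds Dose 3. Only a subject with a new related Grade 3 value at Day 180 would be affected in practice. The documents give no rate for that.

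**The case against.** The strongest reply is that 5.2 and 8.6.2 are the operative rules and 2.3.1 is risk narrative. Section 5.2 leaves laboratory stopping to the individual halting criteria, and under 8.6.2 a single new value at Day 180 cannot meet the persistence condition. On that reading, injecting on the sampling day breaches nothing. This is a coherent reading, but it concedes that the sentence in 2.3.1 is not followed, and 2.3.1 is written as a plain statement of what will happen to subjects. The contradiction remains.

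Three stronger readings are tempting, and the documents do not support them.

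- A reader might infer that the laboratory safeguard cannot work at all. It can. Mandatory Day 8 and Day 36 samples precede Doses 2 and 3, repeats are allowed on Days 15 and 43 and at unscheduled visits, and study-level halting in 8.6.1 covers related Grade 3 laboratory events in the same parameter in two or more subjects.
- A reader might infer that a subject with a Grade 3 value at Day 180 would receive Dose 3 before anyone saw it. No turnaround time is given, handling details sit in a laboratory manual and manual of procedures that are not among the documents, Visit 11 has a ± 14 day window, and nothing forbids waiting. The eligibility review is also listed after the draw. The text supports only that review before injection is not ensured.
- A reader might infer that reading the result after Dose 3 blurs attribution to that dose. It does not: the blood is drawn before the injection, so the value cannot reflect Dose 3.

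**Conclusion.** The point holds in two parts. The conflict between 2.3.1 and 8.6.2 (with SAP 6.6) is plain on the page and needs no assumption: the same subject can be barred under one and eligible under the other. The gap at Visit 11 is that review of the Day 180 result before Dose 3 is not ensured.

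The size of that gap depends on the unstated turnaround time. If results are in practice read before injection, the gap closes. If not, Dose 3 relies on a mandatory sample 144 days old (127 to 161 across the windows). That the Day 180 sample was meant to inform Dose 3 is inferred from its position in 2.3.1.

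This should be corrected because it concerns a rule for withholding vaccine. It is a matter of consistency and missing specification, and does not show that subjects are unprotected.

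**What to change.** Reconcile Protocol 2.3.1, 5.2, 6.3.1.10 and 8.6.2 and SAP 6.6, so that one laboratory halting condition is used throughout. State explicitly whether the Day 180 result must be reviewed before Dose 3, and make 2.3.1, 5.2 and the Visit 11 list agree with that statement. The sponsor decides which clinical rule applies.

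The minimum cost is wording in the protocol and SAP. Any operational cost depends on the rule the sponsor chooses. Sample size and the planned statistical methods are unaffected.
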